9.2.2. Sample Size Sensitivity

Table 9 shows the precision with different sample sizes and different standard deviations.

Table 9 Sample Size Sensitivity

Sample size	Half-width of the 95% confidence interval (SD=1.0)	Half-width of the 95% confidence interval (SD=1.5)
17	0.514	0.771
20	0.468	0.702
22	0.443	0.665

SD = Standard Deviation

9.2.3. Sample Size Re-estimation or Adjustment

No sample size re-estimation is planned in this study.

9.3. Data Analysis Considerations

9.3.1. Analysis Populations

- All Screening Population

The All Screening Population consists of all subjects who are given subject number and whose data are collected, including demographics at screening.

- All Treated Subjects Population

The All Treated Subjects Population will consist of all subjects who received at least one dose of GSK1278863. This population will be used for evaluation of the efficacy, safety and demographic data.

- PK Population

The PK Population will consist of all subjects who received GSK1278863 with the PK samples collected and analyzed.

Additional populations may be defined in the RAP.

9.3.2. Interim Analysis

No interim analysis is planned.

9.3.3. Final Analysis

Once all subjects complete protocol-defined visits, final analysis will be performed after database lock.

9.4. Key Elements of Analysis Plan

9.4.1. Efficacy Analysis

9.4.1.1. Primary Analysis

The primary analysis is to assess modest increase in Hgb in initial response to GSK1278863 (i.e., Hgb increase by ≤ 2 g/dL after 4 weeks of treatment), on the basis of the mean change from baseline in Hgb at Week 4 as well as the number (%) of subjects by Hgb change from baseline category at Week 4 as the primary efficacy endpoints.

For the change from baseline in Hgb at Week 4, the summary statistics will be calculated, along with the two-sided 95% confidence interval based on t-distribution. The change in Hgb at Week 4 will be classified into different categories (i.e., ≤ -2 , > -2 to -1 , > -1 to 0 , > 0 to 1 , > 1 to 2 , and > 2 g/dL), and the number (%) of subjects in each category will be summarized.

9.4.1.2. Secondary Analysis

The secondary analysis is to assess appropriate control of Hgb within the target range, on the basis of the Hgb mean at Week 24 and the number (%) of subjects with Hgb within the target range as secondary endpoints.

For the Hgb at Week 24, the summary statistics will be calculated, along with the two-sided 95% confidence interval based on t-distribution. The percentage of subjects with Hgb within the target range will be calculated at Week 24, with calculation of exact two-sided 95% confidence interval based on binomial distribution. In addition, the time (in days) to reach the lower target Hgb level (10.0 g/dL) will be calculated in each subject, and summarized descriptively.

Also for other secondary efficacy endpoints, such as iron use and iron metabolism, the data will be summarized descriptively.

9.4.2. Safety Analysis

9.4.2.1. Exposure

Exposure information will be listed for all subjects. The duration of treatment (number of days), cumulative dose will be tabulated. In addition, distribution of the dose level at each assessment visit and final assessment visit will be tabulated. Frequency of dose adjustment and duration of treatment interruption due to Hgb >13 g/dL will be summarized.

9.4.2.2. Adverse Events

Adverse events will be classified by System Organ Class and Preferred Term of the MedDRA, and the number and percentage of subjects with each event will be summarized. All adverse events, serious adverse events, adverse events leading to discontinuation of study treatment, and adverse events of special interest will be summarized separately. Similar summary will be provided for adverse events related to GSK1278863.

9.4.2.3. Other Safety Measures

For laboratory tests, vital signs, and ECG, parameters and/or changes from baseline will be summarized using summary statistics at each assessment visit. The number and percentage of subjects with values of the potential clinical importance will be tabulated. The criteria for the potential clinical importance will be described in the RAP. For lipid parameters (total cholesterol, LDL cholesterol, and HDL cholesterol), percent changes will also be tabulated.

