# 2. SUMMARY OF KEY PROTOCOL INFORMATION

## 2.1. Changes to the Protocol Defined Statistical Analysis Plan

No changes from the originally planned statistical analysis specified in the protocol amendment v04 (Dated: 19/Jul/2017) are present.

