### *Worst Case Laboratory Results Relative to Normal Range/PCI Criteria Post-Baseline Relative to Baseline*

The number of subjects with worst laboratory results relative to normal range/potential clinical importance (PCI) criteria which are post-baseline relative to baseline, including unscheduled assessments, will be summarized by test and category. Summaries for normal range and PCI will be provided separately. The categories for normal range are: To Low, To Normal or No Change, To High; the categories for PCI criteria are: To Low, To w/in Range or No Change, To High. The categorization is determined by comparing the baseline category to the worst case post-baseline category.

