#### • Vital Signs

Vital sign values will be summarized using mean, standard deviation, minimum, median, and maximum for each assessment visit. Separate summary statistics of pre- and postdialysis vital signs will be provided for raw values and change from baseline. In a summary of change from baseline, each baseline value (i.e. pre- and post-dialysis baseline) will be used for calculation (Section 10.5.2).

The number of subjects with worst case vital sign results relative to PCI criteria which are post-baseline relative to baseline, including unscheduled assessments, will also be summarized by test and category. The categories for PCI criteria are: To Low, To w/in Range or No Change, To High. The categorization is determined by comparing the baseline category to the worst case post-baseline category.

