3.21.	All Treated Subjects	AE1	Summary of AEs Leading to Withdrawal from Study / Permanent Discontinuation of Study Treatment by SOC and PT	IDSL	Y			
AEs of	Special Inter	est		·				
3.22.	All Treated Subjects	SAFE_T1	Summary of On-Therapy AEs of special interest		Y			
3.23.	All Treated	SAFE_T1	Summary of On-Therapy AEs of special interest by Dialysis Status		Y			

Safety	Safety : Tables							
No.	Populatio n	IDSL / TST ID / Example Shell	Title	Programming Notes	SAC			
	Subjects							
3.24.	All Treated Subjects	SAFE_T1	Summary of Post-Therapy AEs of special interest		Y			
Labora	atory Chemist	ry						
3.25.	All Treated Subjects	LB1	Summary of Chemistry Values by Visit	ICH E3 Includes Baseline values	Y			
3.26.	All Treated Subjects	LB1	Summary of Chemistry Changes from Baseline by Visit	ICH E3	Y			
3.27.	All Treated Subjects	SAFE_T2	Summary of Percent change from Baseline in Lipid Parameters (total cholesterol, LDL cholesterol and HDL cholesterol) by Visit		Y			
3.28.	All Treated Subjects	LB15	Summary of Worst Case Chemistry Results Relative to Normal Range Post-Baseline Relative to Baseline	ICH E3	Y			
3.29.	All Treated Subjects	LB17	Summary of Worst Case Chemistry Results Relative to PCI Criteria Post-Baseline Relative to Baseline	ICH E3	Y			
Hemat	ology							
3.30.	All Treated Subjects	LB1	Summary of Hematology Values by Visit	ICH E3 Includes Baseline values	Y			
3.31.	All Treated Subjects	LB1	Summary of Hematology Changes from Baseline by Visit	ICH E3	Y			
3.32.	All Treated Subjects	LB15	Summary of Worst Case Hematology Results Relative to Normal Range Post-Baseline Relative to Baseline	ICH E3	Y			
3.33.	All Treated Subjects	LB17	Summary of Worst Case Hematology Results Relative to PCI Criteria Post-Baseline Relative to Baseline	ICH E3	Y			
Other	Laboratory Te	ests		·				
3.34.	All Treated	LB1	Summary of Other Laboratory Values by Visit	ICH E3	Y			

Safety	Safety : Tables						
No.	Populatio n	IDSL / TST ID / Example Shell	Title	Programming Notes	SAC		
	Subjects			Includes Baseline values			
3.35.	All Treated Subjects	LB1	Summary of Other Laboratory Changes from Baseline by Visit	ICH E3	Y		
3.36.	All Treated Subjects	LB15	Summary of Worst Case Other Laboratory Results Relative to Normal Range Post-Baseline Relative to Baselinet	ICH E3	Y		
3.37.	All Treated Subjects	LB17	Summary of Worst Case Other Laboratory Results Relative to PCI Criteria Post-Baseline Relative to Baseline	ICH E3	Y		
Hepato	biliary (Liver						

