3.38.	All Treated Subjects	LIVER1	Summary of Liver Monitoring/Stopping Event Reporting	IDSL	Y		
3.39.	All Treated Subjects	LIVER10	Summary of Subjects Meeting Emergent Hepatobiliary Laboratory Abnormality Criteria	IDSL Listing may be sufficient if few events.	Y		
ECG				-			
3.40.	All Treated Subjects	EG1	Summary of ECG Findings	IDSL	Y		
3.41.	All Treated Subjects	EG2	Summary of Change from Baseline in ECG Values by Visit	IDSL	Y		
Vital S	igns						
3.42.	All Treated Subjects	SAFE_T3 based on VS1	Summary of Vital Signs by Visit	Summarized by each assessment status (i.e. pre-dialysis and post-dialysis)	Y		
3.43.	All Treated Subjects	SAFE_T3 based on VS1	Summary Change from Baseline in Vital Signs by Visit	Summarized by each assessment status (i.e. pre-dialysis and post-dialysis)	Y		
3.44.	All Treated Subjects	SAFE_T4 based on VS7	Summary of Worst Case Vital Sign Results Relative to PCI Criteria Post-Baseline Relative to Baseline	Summarized by each assessment status (i.e. pre-dialysis and post-dialysis)	Y		
Ophth	Ophthalmology						

Safety	Safety : Tables							
No.	Populatio n	IDSL / TST ID / Example Shell	Title	Programming Notes	SAC			
3.45.	All Treated Subjects	SAFE_T5	Summary of Ophthalmologic Exams at Screening		Y			
3.46.	All Treated Subjects	SAFE_T6	Summary of On-Therapy Ophthalmologic Exams		Y			
Safety	Summaries f	or a Plain Langua	ge Summary					
3.47.	All Treated Subjects	AE3	Summary of On-Therapy Serious Drug-Related AEs		Y			
3.48.	All Treated Subjects	AE3	Summary of On-Therapy Non-Serious Drug-Related AEs		Y			

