8.1.2 Planned Efficacy Table Displays	Added the following clarifications in a model specification of Kaplan Meier Method: Subjects within target range at baseline will be excluded from the summary. Subjects who could not reach lower target will be regarded as censored at EoT. In addition, in dose adjustment summary, it has been clarified that what subjects will be included in summaries of duration of treatment interruption and number of dose adjustments.	Clarification	
8.1.2 Planned Efficacy Table Displays	Added summary tables and planed displays detail for number (%) of subjects with each dose level by visit	Tables corresponding to histogram of dose level by visit (Fig. 2.10) are necessary.	
8.2.1.1 Planed AE Analyses Displays	
 
Clarifications were made for the maximum intensity of AEs category and how to treat different intensities in the same AE.
 
It has been modified how to display serious adverse event, for both primary system organ class and preferred term.
 
	
 
Clarification
 
SOC for SAE summary provides a consistent presentation style that facilitates review
 
	

8.2.2 Overview of Planned

Clinical Laboratory Analyses

8.2.3 Overview of Planned

Other Safety Analyses

	Updates were made to the summaries for normal range/PCI criteria. Only the worst case results relative to normal range/PCI criteria post-baseline relative to baseline will be provided.	IDSL templates based on GSK Core RAP requirements in the RAP template are updated.	

 
8.2.3.1 Planned Other Safety
 
Analyses Displays
 
10.5.2 Baseline Definition &
 
Derivations
 
10.14.6 Safety Tables
 
	Updates were made to the indicated sections of RAP to describe how to summarize vital sign assessment. Pre- and post-dialysis assessment will be summarized separately and non-dialysis assessment will not be summarized.	Vital sign assessment in non-dialysis day would be unlikely, so summarization would not be necessary.	
8.2.3.1 Planned Other Safety Analyses Displays	Text added to make sure the summary display for ECG findings.	Clarification	
8.2.3.1 Planned Other Safety Analyses Displays	Additional summary added to ophthalmology exam, displayed along with a summary of on- therapy ophthalmology exam. No additional table is required for this update.	Worthwhile to add another way of summarization	

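### The SAP's tables for values of potential clinical importance merge 'no change' with 'within range', so they do not give the count of affected subjects that the protocol promises

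*Protocol*

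**What the plan says.** **Protocol.** Section 9.4.2.3 covers laboratory tests, vital signs and ECG, and states: "The number and percentage of subjects with values of the potential clinical importance will be tabulated". The sentence is not limited to new onset or to change from baseline. What it leaves to the SAP is the criteria.

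**SAP, laboratory.** In section 8.2.2.1, "the categories for PCI criteria are: To Low, To w/in Range or No Change, To High". The rule for placing a subject follows: "The categorization is determined by comparing the baseline category to the worst case post-baseline category".

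**SAP, vital signs.** Section 8.2.3.1 uses the same three rows and the same rule.

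**SAP, list of displays.** Section 10.14.6 lists four PCI tables, all in this format: 3.29 ("Summary of Worst Case Chemistry Results Relative to PCI Criteria Post-Baseline Relative to Baseline"), 3.33 and 3.37 (the hematology and other-laboratory counterparts) and 3.44 ("Summary of Worst Case Vital Sign Results Relative to PCI Criteria Post-Baseline Relative to Baseline").

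**SAP, departures.** Section 2.1 reports "No changes from the originally planned statistical analysis specified in the protocol amendment v04".

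**SAP text that points the other way.** Section 10.6.1 refers to a row for any post-baseline visit, in which a subject with both high and low values is counted under each, and extends it to the relevant PCI tables.

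**The concern.** The protocol promises a prevalence: how many subjects had a PCI value. The SAP delivers a shift: how many moved into a PCI category they were not in at baseline. The two agree only if nobody is beyond a limit before dosing.

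That cannot be assumed here. The eligibility criteria in Protocol 5.1 and 5.2 set no numerical limit on blood pressure, potassium, phosphate, calcium or iPTH, and SAP Appendix 8 sets PCI limits for all of them. A subject with a systolic pressure of 185 mmHg at baseline and 215 mmHg on treatment is above the 180 mmHg limit both times, so the rule calls this no change and the table places it beside subjects who stayed within limits.

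Laboratory tests and vital signs are stated safety endpoints. The study has one arm and about 22 subjects, so no comparator would show what the merged row conceals. The error runs one way: it makes the abnormality table look more favourable.

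**Working it through.** The plan states no figure to reproduce here. The check is to apply the SAP's rule to every possible case and compare the result with the protocol's count.

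**Step 1. Apply the rule.** For a parameter with a lower and an upper PCI limit there are 3 × 3 = 9 combinations of baseline and worst post-baseline category.

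| Baseline | Worst post-baseline | SAP row | PCI value after baseline? |
|---|---|---|---|
| Low | Low | merged row | **yes** |
| Low | Within | merged row | no |
| Low | High | To High | yes |
| Within | Low | To Low | yes |
| Within | Within | merged row | no |
| Within | High | To High | yes |
| High | Low | To Low | yes |
| High | Within | merged row | no |
| High | High | merged row | **yes** |

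Six combinations have a PCI value after baseline. Four of them appear as To Low or To High, including both crossings from one limit to the other. The remaining two, Low to Low and High to High, share the merged row with the three combinations that have no PCI value after baseline. The table gives one total for those five, so the protocol's count cannot be worked back from it.

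**Step 2. Look for the count elsewhere in the SAP.**

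- *Other PCI tables:* none is listed in section 10.14.6. The amendment log in section 10.16 agrees: "Only the worst case results relative to normal range/PCI criteria post-baseline relative to baseline will be provided".
- *The any-visit row of section 10.6.1:* it would supply the count, but no display described in section 8.2 contains it. The mock shells are in separate documents (section 10.15) and were not available to check.
- *Listings:* 26–28 (laboratory) and 56 (vital signs) show the individual values. They are not a tabulated number and percentage, and 26–28 also include subjects who are only outside the normal range.
- *Liver tables 3.38 and 3.39:* these do not cover blood pressure, electrolytes, phosphate or iPTH.

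**Step 3. Illustrate the size.** The documents give none of the rates needed, so all three below are assumptions. Take one direction of one parameter with N = 22, the planned enrolment in Protocol 9.2.1. Let

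- b = share beyond the limit at baseline;
- r = share of those with at least one post-baseline value still beyond the same limit, 0.8 to 1.0;
- q = share of the others who newly go beyond it, 0.1.

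Protocol count = 22 × [(1 − b)q + br]. SAP shift row = 22 × (1 − b)q. Shortfall = 22 × br.

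| b | Protocol count (r = 0.8 to 1.0) | SAP shift row | Shortfall |
|---|---|---|---|
| 0.1 | 22 × (0.09 + 0.08 to 0.10) = 3.7 to 4.2 | 22 × 0.09 = 2.0 | 1.8 to 2.2 |
| 0.3 | 22 × (0.07 + 0.24 to 0.30) = 6.8 to 8.1 | 22 × 0.07 = 1.5 | 5.3 to 6.6 |
| 0.5 | 22 × (0.05 + 0.40 to 0.50) = 9.9 to 12.1 | 22 × 0.05 = 1.1 | 8.8 to 11.0 |

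The values depend on the assumptions. The direction does not: with q and r fixed, a higher baseline share lowers the reported row and widens the shortfall.

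**The case against.** **Section 10.6.1 may already provide the count.** Appendix 14 gives titles and shell identifiers, not rows, so its silence does not prove that the any-visit row is absent. This stands in part: with the shells unseen, one cannot say that the final output will lack the row. But sections 8.2.2.1 and 8.2.3.1 define the categories without it, and the amendment log says only the worst-case-relative-to-baseline format is produced. The texts conflict and need reconciling.

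**The data are reported anyway.** This stands. Besides the listings, the by-visit tables give the maximum and the change from baseline, so 215 mmHg at a scheduled visit would show there. A reader might infer that deterioration is hidden altogether. The documents do not support that; what is missing is the tabulated count.

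**A shift table is a sound display in a single-arm study.** It separates new from pre-existing abnormality, and the protocol leaves detail to the SAP. That justifies keeping the shift rows. It does not justify merging persistent abnormality with normality, or omitting the count the protocol names. Protocol section 9 allows departures if they are documented in the SAP or the final report; SAP 2.1 records none.

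**Baseline PCI values may be rare for some parameters.** This is fair. For ALT and bilirubin, the screening exclusions (above 2 and 1.5 times the upper limit, with an exception for fractionated bilirubin) lie below the PCI limits (3 and 2 times). The limits for iPTH (above 9 times the upper reference limit) and potassium (more than 1.0 mmol/L above it) are wide. The gap will matter for some parameters and not for others.

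**Hemoglobin.** Every subject enters with a HemoCue value below 10.0 g/dL, so a reader might infer that falls in hemoglobin vanish from normal-range Table 3.32. That should not be argued. Hemoglobin has no PCI limit in SAP 10.8.1, so the protocol sentence does not reach it. Falls are covered by the count below 7.5 g/dL, the count below target range, and the by-visit values and changes.

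**Conclusion.** The point holds in this form: the four PCI tables, as defined in SAP 8.2.2.1 and 8.2.3.1, do not give the number and percentage of subjects with PCI values that Protocol 9.4.2.3 promises, and SAP 2.1 does not declare the difference. The affected subjects are those beyond a limit at baseline who have a post-baseline value beyond the same limit. It would go too far to say that everyone outside the limits at baseline is miscounted, because those who cross to the opposite limit are counted and those who return to range are correctly not counted.

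The structural result needs no numerical assumption; it follows from the stated rule. It is subject to one reservation, that the unseen shells might contain the row mentioned in section 10.6.1. The size is unknown, because the documents report no baseline PCI rates; the shortfalls of about 2 to 11 subjects out of 22 are illustrative. No efficacy estimate is affected. This is a gap in the safety tabulation that errs in the favourable direction, and it is worth closing before the tables are produced.

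**What to change.** In SAP 8.2.2.1 and 8.2.3.1, and in the shells for Tables 3.29, 3.33, 3.37 and 3.44:

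1. For each parameter and direction, add the n (%) of subjects with any post-baseline PCI value, overall and split by baseline status (within limits, or already beyond that limit).
2. Split the merged row so that 'no change, already outside limits' stands apart from 'to within range'.
3. Reconcile section 10.6.1 with these sections, by adding its any-visit row to the described displays or by removing the reference.

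If the sponsor prefers to keep the tables as they are, SAP 2.1 should declare the departure and give the reason.

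The cost is a few extra table rows from data already collected, and reported abnormality counts that will look less favourable. The split by baseline status keeps pre-existing abnormality from being read as a drug effect.

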9.4.3. Pharmacokinetic Analysis

For plasma concentrations of GSK1278863 over time, individual data will be listed, and summary statistics at each time point will be calculated by each dose level. For PK parameters (AUC 0-4 and Cmax), summary statistics will be calculated by each dose level, and scatter plots against the dose level will be generated.

10. STUDY GOVERNANCE CONSIDERATIONS

10.1. Posting of Information on Publicly Available Clinical Trial Registers

Study information from this protocol will be posted on publicly available clinical trial registers before enrollment of subjects begins.

10.2. Regulatory and Ethical Considerations, Including the Informed Consent Process

The study will be conducted in accordance with “the Ministerial Ordinance on the Standards for the Conduct of Clinical Trials of Medicinal Products (MHW Notification No.28 dated 27th March, 1997)” and the Pharmaceutical Affairs Law.

GSK will submit the CTN to the regulatory authorities in accordance with Article 80-2 of the Pharmaceutical Affairs Law before conclusion of any contract for the conduct of the study with study sites.

The study will be conducted in accordance with all applicable regulatory requirements, and with GSK policy.

The study will also be conducted in accordance with ICH Good Clinical Practice (GCP), all applicable subject privacy requirements, and the guiding principles of the current version of the Declaration of Helsinki. This includes, but is not limited to, the following:

- IRB/IEC review and favorable opinion/approval of the study protocol and amendments as applicable
- Signed informed consent to be obtained for each subject before participation in the study (and for amendments as applicable)
- Investigator reporting requirements (e.g. reporting of AEs/SAEs/protocol deviations to IRB/IEC)
- GSK will provide full details of the above procedures, either verbally, in writing, or both.
- The IEC/IRB, and where applicable the regulatory authority, approve the clinical protocol and all optional assessments, including genetic research.
- Optional assessments (including those in a separate protocol and/or under separate informed consent) and the clinical protocol should be concurrently submitted for approval unless regulation requires separate submission.
- Approval of the optional assessments may occur after approval is granted for the clinical protocol where required by regulatory authorities. In this situation, written approval of the clinical protocol should state that approval of optional assessments is being deferred and the study, with the exception of the optional assessments, can be initiated.

Informed Consent

Prior to participation in the study, the investigator (or subinvestigator) should fully inform the potential subject and the subject's legally acceptable representative (as required) of the study including the written information. The investigator (or subinvestigator) should provide the subject and the subject's legally acceptable representative enough time and opportunity to inquire about details of the study. The subject and the subject's legally acceptable representative should sign and personally date the consent form. If the subject wishes to consider the content of the written information at home,

he/she may take the consent form home. The person who conducted the informed consent discussion and study collaborator giving supplementary explanation, where applicable, should sign and personally date the consent form. If an impartial witness is required, the witness should sign and personally date the consent form. The investigator (or subinvestigator) should retain this signed and dated form (and other written information) together with the source medical records, such as clinical charts (in accordance with the rules for records retention, if any, at each medical institution) and give a copy to the subject and the subject's legally acceptable representative.

